4 STUDY DESIGN

4.1 OVERALL DESIGN

We will perform a two-arm RCT among a geographically diverse group of patients with mixed-etiology chronic pain. Using a random number generator, patients will be allocated in a 1:1 ratio at the site level between two self-administered, remotely deployed CBT delivery platforms: (1) a 2D mHealth app called PainTRAINER; and (2) 3D VR app called EaseVRx. The primary analysis will compare changes in pain intensity over 8 weeks upon completion of the standardized 8-week digital CBT protocols. Secondary outcomes will include pain catastrophizing, pain interference, self-efficacy, anxiety, and opioid use. Patient blinding is not possible in VR versus non-VR studies; we will explain the purpose of our study is to determine if one of two self-taught pain-management skills programs is more effective in helping manage pain, alongside current treatment. If so, how much more effective is it and which patients does the program help the most? Both programs have been proven effective; in other words, both programs have been studied and results for both showed improvement in patients' ability to manage their pain. To do this, participants will be randomly assigned to test either a virtual reality (VR) program called EaseVRx or an online/mobile program called painTRAINER. Because it is important for researchers to exhibit equipoise when describing the competing interventions, we will prepare a script that uses neutral language regarding the two interventions, as per previous VR research. In addition, data analysts will be blinded to patient allocation.

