5.5 STRATEGIES FOR RECRUITMENT AND RETENTION

The target sample size is 300. The population impacted by this research broadly encompasses individuals with many different types of chronic pain conditions, including somatic, musculoskeletal, neuropathic, and visceral pain. Using data from the Federal Office of Rural Health Policy (FORHP), rural Louisiana has a high prevalence of nearly 32% non-Hispanic Black, rural California has 2.5%, and Alabama 22.7%. We will oversample with a target of 20% for non-Hispanic Blacks in this study. We will have a monitoring plan to ensure that we maintain our 20% goal throughout conduct of the study. Rural California is 30% Hispanic, while Alabama and Louisiana have fewer than 2% Hispanic rural populations. The mean across states is 11.2%. The national mean of rural Hispanic populations is 6.6%. Because we will likely receive more patients from Alabama and Louisiana than from California (because there are two sites in the Deep South vs. one in urban California), we anticipate a weighted mean of closer to 8% Hispanic and will therefore target this value for our study.

All four clinical sites have patient cohort search engines that will be used to identify patients with chronic pain. The informatics department at each site will pull zip code data for each potential participant, which will be matched with year 2010 RUCA zip codes provided by the USDA. This will provide a list of all possible participants that meet our desired criteria. We will monitor enrollment monthly and use the list to enrich enrollment as needed throughout the study to maintain the 20% target for the overall sample (across all three States).

Across the four recruitment sites (Cedars-Sinai, Ochsner, UAB, Bendcare) over 10,000 patients are designated as being in a rural area. Though all four sites are based in urban location. There is a significant amount of rural area surrounding each area. Note that [name] from University of Alabama is associated with Bendcare and the UAB coordinator will serve the same role for patients identified from Bendcare.

Recruitment for the proposed trial will be maximized using several strategies:

- Patients will be screened over a period of 24 months. Due to the COVID-19 pandemic, remote recruitment, which we have implemented and proved to be effective in our previous VR trials, will supplement in-person recruitment to ensure that we can reach the target enrollment goal.

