9.2 SAMPLE SIZE DETERMINATION

Sample Size calculations and Power Estimation

Sample Size calculations and Power Estimation

Sample Size Calculation: The primary goal of the study is to test the effectiveness of *PainTRAINER* vs. *EaseVRx*, in reducing pain intensity. The trial will be testing if there is statistical evidence that either *PainTRAINER* or *EaseVRx* is more effective in lowering average weekly pain intensity after 8 weeks from start of intervention. We estimate power to assess the effect of the

Table 1. Minimum detectable odds ratio as a function of the proportion of variability in treatment type that is explained by all other relevant covariates in the model and the baseline probability of positive treatment response.

Baseline probability	R ²			
	0.0	0.1	0.2	0.4
0.2	2.32	2.42	2.55	2.91
0.3	2.17	2.25	2.37	2.69
0.5	2.15	2.25	2.37	2.74

interventions on the treatment response (achievement of a minimally clinically important difference [MCID] of 2.0 on the NRS^{56,57} (y/n)) using logistic regression, accounting for possible confounding factors for the primary outcome described in Aim 1. The dependent variable is the treatment response and the main independent variable of interest is *PainTRAINER* vs. *EaseVRx*. **Table 1** displays the minimum odds ratio that can be detected with 90% power with the two-sided 0.05 level of significance as a function of baseline probability of positive response when a patient is treated with *EaseVRx* and R², the proportion of variability in the predictor of interest that is explained by all relevant baseline covariates in the model using data from 150 patients in the *PainTRAINER* arm and 150 in the *EaseVRx*. For example, data from 300 patients achieve 90% power to detect an odds ratio of 2.25 if the probability of positive response when a patient is treated with *PainTRAINER* is 0.3 and 0.1 of the variability in intervention is explained by all other baseline covariates in the model. These odds ratios vary between 2.15 and 2.91 and are clinically meaningful. Therefore, we have enough power to test statistical significance of predictors in the multivariable logistic regression model. Regarding clinical significance, given an MCID of 2 points on the NRS and a SD of 2 on this scale from our own digital health trials, data from 150 patients in each group

will achieve 90% power to detect a mean pain intensity score difference of 0.75, corresponding to a clinically meaningful effect size of 0.38 SD.

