9.4.7 EXPLORATORY ANALYSIS

The purpose of Aim 2, as described in the application, is to detect heterogeneity of treatment effect (i.e. differential response to the same treatment due to individual traits) on pain intensity by PainTRAINER or EaseVRx. The results will enable the research team to work with patient partners to make recommendations for optimizing deployment of home-based digital behavioral treatment across a diverse populace. We will investigate the predictive value of key patient characteristics, including type of pain condition, sex, age, race, ethnicity, State and zip code, Rural- Urban Commuting Area (RUCA) codes (a composite measure of population density, urbanization, and daily commuting), pain severity, opioid use, comorbidities, social support, and COVID-19 impacts (unemployment, financial hardship, family or personal COVID-19 diagnosis). The analysis for each covariate will consist of an unadjusted test of interaction with treatment group in a multivariate logistic regression model with responder status (subject achieved MCID difference or did not) as the dependent variable. These models will include fixed categorical effects for treatment, covariate, and treatment-by-covariate interaction. Interaction terms with a significance level of less than .10 will be included in full model testing. The p-values of interaction terms will be presented, as will the odds ratios and 95% confidence intervals by treatment and covariate. If multiple interaction terms demonstrate a significance level of less than .10, we will use a least absolute shrinkage and selection operator (LASSO) approach to variable selection. We will also use multivariable logit modeling with receiver operator characteristic (ROC) curve analysis to measure the accuracy of the resulting model in predicting achievement of an MCID response as measured by the area under the ROC curve by c-statistic.

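### The exploratory Aim 2 c-statistic is scored on the same patients used to screen and select the model, with no internal validation, so it is likely to be biased upward

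*Combined protocol and SAP*

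**What the plan says.** Section 9.4.7 lists patient characteristics under 12 headings and tests each one separately for interaction with treatment, in a logistic model for achieving the MCID. Covariates enter as categorical effects. The carry-forward rule is: "Interaction terms with a significance level of less than .10 will be included in full model testing". If more than one interaction passes, LASSO is used to choose among them. ROC analysis of a multivariable logistic model then serves to "measure the accuracy of the resulting model in predicting achievement of an MCID response", expressed as the c-statistic. The results are meant to feed recommendations, made with patient partners, on deploying home-based digital treatment.

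No validation step is attached to this chain. The only bootstrap planned for an analysis is in Section 9.4.3, for confidence intervals on MME differences. Validation in Section 10.1.7 means data-entry checks, and in Table 2 it refers to diagnosis codes. Section 9.4.1 controls the family-wise error rate for primary and secondary endpoints only, and leaves model-building tests outside the gatekeeping.

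On size, Section 5.5 states "The target sample size is 300". Section 9.4.7 gives no sample-size reasoning for Aim 2 and no expected c-statistic.

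**The concern.** A c-statistic computed on the data that chose the model rewards the model for fitting noise. Here the outcome is used three times: to pick the interactions, to estimate their coefficients, and to score the predictions. Each use pushes the figure above what new patients would show.

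This matters because finding out which patients respond to which program is a stated study goal (Sections 1.1, 2.1 and 4.2), and Aim 2 is the analysis that addresses it. A published c-statistic of about 0.6, with a confidence interval clear of 0.5, would be read as evidence that response can be predicted from baseline traits. The exploratory label tells readers to be cautious about a claim. It does not remove bias from a number.

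**Working it through.** **1. Inputs from the plan.** N = 300, allocated 1:1 (Sections 5.5 and 4.1). Response probabilities 0.2, 0.3 and 0.5 (rows of Table 1, Section 9.2), i.e. 60, 90 or 150 responders. Screening threshold 0.10.

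**2. Assumptions, because the plan is silent.** There are 12 covariates if each listed heading counts once. There are 16 if State and zip code are separated (+1) and the COVID-19 impacts are split into four items (+3). Covariates are either all binary or have mixed levels, from 2 to 7. Seven levels would fit RUCA codes 4 to 10, the range admitted by Section 5.1. The LASSO penalty is chosen by 5-fold cross-validation and the model refitted.

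**3. The plan's own figures reproduce.** Section 9.2 claims "90% power to detect a mean pain intensity score difference of 0.75" with SD 2. Per arm, 2 × (1.960 + 1.282)² × 2² / 0.75² = 149.4, so 150; power at 150 per arm is 0.901. For Table 1, p2 = OR × p1 / (1 + p1 × (OR − 1)), with N inflated by 1/(1 − R²). At p1 = 0.3, OR 2.25 and R² = 0.1, p2 = 0.675/1.375 = 0.491, total N is 303 and power at 300 is 0.898. All 12 cells agree (N 300 to 304, power 0.898 to 0.902). These figures concern the treatment comparison; none addresses Aim 2.

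**4. False interactions when nothing predicts response (independent tests).**

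| Covariates | Expected false passes | P(at least one) | P(two or more) |
|---|---|---|---|
| 12 | 1.2 | 1 − 0.9^12 = 0.72 | 0.34 |
| 16 | 1.6 | 1 − 0.9^16 = 0.81 | 0.49 |

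P(two or more) = 1 − 0.9^k − k × 0.1 × 0.9^(k−1). By these figures the LASSO step would be triggered in only 34% to 49% of null trials; a lone survivor goes forward without it. In the main simulations (200 to 400 trials each, likelihood-ratio tests), at least one term passed in 73.5% to 87% of trials.

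**5. Same-sample c-statistic under that null.** The model was scored on its own patients and on a large fresh sample. Trials with no selected term are included.

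| Final model | Mean c, same patients | Naive 95% CI excludes 0.5 |
|---|---|---|
| Screened terms, no LASSO, 16 binary, response 0.2 to 0.5 | 0.60 to 0.61 | 72% to 80% |
| Screened terms, no LASSO, 16 mixed, response 0.2 to 0.5 | 0.61 to 0.64 | 79% to 83% |
| With LASSO and refit, 12 binary, response 0.3 | 0.57 | 48% |
| With LASSO and refit, 16 binary, response 0.3 | 0.58 | 62% |
| With LASSO and refit, 16 mixed, response 0.3 | 0.59 | 60% |
| All main effects plus selected interactions, 16 binary | 0.66 to 0.70 | not computed |
| All main effects plus selected interactions, 16 mixed | 0.72 to 0.78 | not computed |

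The fresh-sample value was 0.500 in every scenario above. Separate no-LASSO runs with 12 to 16 binary covariates gave 0.58 to 0.62. A further run with all main effects kept, 13 to 15 covariates (half binary, half normal) and 35% responders gave 0.65 to 0.66. At N = 240 (an assumed shortfall; mixed levels, LASSO, response 0.3) the mean was 0.59.

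**6. Does correction work?** Corrected c = apparent c minus the mean over resamples of (c of the resample's model in that resample, minus c of the same model in the original data), with screening and fitting redone each time. With 16 covariates, response 0.3, no LASSO, 60 trials and 40 resamples each, the mean fell from 0.608 to 0.515 (binary) and from 0.644 to 0.504 (mixed). The correction was not run with LASSO included.

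**The case against.** The best defence has four parts.

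- *The plan uses LASSO, which shrinks noise.* This stands in part. LASSO lowers the mean from about 0.60 to 0.63 to about 0.58 to 0.59 (16 covariates, response 0.3), so quoting only no-LASSO figures would overstate the bias. It does not remove it, because it runs only after a screen on the same outcome, and tuning the penalty by cross-validation does not validate the whole sequence.
- *The size depends on modelling choices the plan leaves open.* This stands. Covariate coding, the penalty rule, retention of main effects and the model used when nothing passes are all unspecified. A reader might infer that c-statistics well above 0.65 are typical. On average they arise only if all main effects are kept, and the full model named in Section 9.4.7 is not defined that way.
- *The result would not necessarily look predictive.* This stands. In roughly 13% to 28% of null trials no interaction passes, LASSO can remove those that do, and c then stays near 0.5. Whether 0.57 to 0.59 looks predictive is a judgement. An upward bias is likely; a misleading figure in every trial is not.
- *The analysis is exploratory.* This limits the consequence. A reader might infer that an inflated c-statistic would by itself justify matching patients to programs. It would not: it measures how well MCID response is predicted, and a model can do that without showing who gains more from one program than the other. Section 9.4.7 also reports interaction p-values and odds ratios with intervals.

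**Conclusion.** The concern holds in limited form. As written, the Aim 2 c-statistic is likely to be biased upward, because screening, selection and scoring share one set of patients and nothing corrects for it. When nothing predicts response, the mean apparent value is about 0.58 to 0.64 for screened terms without LASSO and about 0.57 to 0.59 with LASSO at response 0.3, against a true 0.50. These sizes rest on 12 to 16 independent covariates with assumed levels, N = 300 and a global null; the direction was the same under every reading tried. The figure of 300 is the enrolment target, and fewer patients with week 8 data would not help.

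The documents do not support extending this to the trial's main results. The primary and secondary analyses do not use the Aim 2 model, so their conclusions are untouched. This is a change the sponsor should make, not one on which the trial depends.

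**What to change.** State in Section 9.4.7 that the entire sequence (interaction screening, LASSO when triggered, and final fitting) will be repeated inside each bootstrap resample or each fold of repeated cross-validation, and that the optimism-corrected c-statistic is the accuracy result. The apparent value may be shown beside it, labelled as such.

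Fix in advance the coding and number of levels of each covariate, the LASSO penalty rule, whether main effects stay in the final model, and what is reported if no interaction passes.

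Replacing the p < .10 screen with a single penalised model holding all listed interactions is optional. A simple screen is acceptable in an exploratory analysis once the accuracy figure is corrected, and one penalised model would not directly give the planned per-covariate interaction p-values.

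The cost is some programming time, a few lines of text and a lower reported c-statistic. Enrolment, data collection and the primary analysis are unchanged.

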The study will recruit 300 people from rural communities in California, Louisiana, Florida, and Alabama and randomize them into either the 2D or 3D programs. We will then follow patients for 8 weeks and measure their pain levels. We will also measure signs of distress, including anxiety, along with medications used for pain, such as opioids, and the impact of pain on overall quality of life. To conduct the study, we will ask patients to periodically complete short surveys online and give their permission for the research team to collect information from the electronic health record. We developed this study working with patient partners from the American Chronic Pain Association (ACPA), and they will be part of the research team throughout the conduct, analysis, and reporting of the study. The results will help patients, doctors, and health system decide which homebased, patient-administered, digital treatment programs for pain to choose, better enabling providers to select the right treatment for the right patient.

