9.4 STATISTICAL ANALYSES

9.4.1 GENERAL APPROACH

All statistical analyses will be performed jointly by the Cedars-Sinai Biostatistics Core and the Cedars-Sinai Center for Outcomes Research and Education (CS-CORE) using SAS® software version 9.3 or higher (SAS Institute, Cary, NC, USA), R version 3.5.0 or higher (R Foundation for Statistical Computing, Vienna, Austria) or Stata software version 14 or higher (StataCorp LLC, College Station, TX, USA). Continuous variables will be summarized using descriptive statistics (N, mean, standard deviation, minimum, median, and maximum as appropriate). Categorical variables will be summarized using the number and percentage of patients in each category. Data will be summarized with respect to patient demographic and baseline characteristics both across the study and by study-arm. The efficacy endpoints, safety assessments, and other outcome results for each treatment group will be summarized descriptively unless otherwise indicated. In addition, statistical model estimates of least squares means, treatment differences, p-values and 95% confidence intervals will also be provided where relevant. The fit of general linear models will be assessed using residual plots and/or other diagnostic plots as appropriate. The fit of logistic models will be assessed using Hosmer-Lemeshow goodness-of-fit and/or receiver operating characteristic (ROC) curves as appropriate. All statistical tests will be 2-sided and performed at the 0.05 level of significance unless stated otherwise.

Multiple Comparisons/Multiplicity: The family-wise type I error rate (FWER) for the statistical tests of the primary and secondary endpoints will be controlled at 0.05. To strongly control the FWER at this level, a gatekeeping approach will be utilized. A closed testing procedure will be employed to control the FWER. Any hypothesis tests conducted for model building purposes will be conducted outside of any gatekeeping.

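### The only accuracy measure named for the final Aim 2 model is a c-statistic for response; nothing measures whether the combined model helps choose between EaseVRx and PainTRAINER

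*Combined protocol and SAP*

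**What the plan says.** Section 9.4.7 states that the purpose of Aim 2 "is to detect heterogeneity of treatment effect (i.e. differential response to the same treatment due to individual traits) on pain intensity". It says the results will support recommendations on how to deploy the two programs. Section 2.1 puts the intended use as "better enabling providers to select the right treatment for the right patient".

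The method has three parts:

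- Each patient characteristic is tested for interaction with treatment in a logistic model for achieving the 2-point MCID. "Interaction terms with a significance level of less than .10 will be included in full model testing". LASSO is used for selection if several terms pass.
- "The p-values of interaction terms will be presented, as will the odds ratios and 95% confidence intervals by treatment and covariate".
- Last, a multivariable logit model with ROC analysis is used to "measure the accuracy of the resulting model in predicting achievement of an MCID response as measured by the area under the ROC curve".

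For logistic models generally, section 9.4.1 adds: "The fit of logistic models will be assessed using Hosmer-Lemeshow goodness-of-fit and/or receiver operating characteristic (ROC) curves as appropriate". Section 9.4.1 also plans a treatment-by-sex interaction test in a mixed model. No section plans a measure of how well a model predicts benefit from one program over the other.

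**The concern.** A c-statistic for response is the probability that a randomly chosen responder has a higher predicted probability than a randomly chosen non-responder, whichever program each received. Prognosis feeds it as readily as heterogeneity does. Pain severity, opioid use and comorbidities are on the 9.4.7 covariate list and could plausibly be prognostic. A model with no value for choosing a program could therefore show a respectable c, and a model that captures opposite effects in different patients could show a modest one. This is true of the correct model in an infinite sample, so validation against over-fitting would not remove it.

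What is at stake is the advice on matching patients to programs. The interaction outputs look at one covariate at a time. Once several terms are combined, no planned quantity says whether acting on the model would raise the response rate.

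**Working it through.** **Inputs.** From section 9.2: 300 patients, 150 per arm, and a worked example with response probability 0.3, R² 0.1 and odds ratio 2.25. From section 9.4.7: the p<.10 screen. Prognostic strengths, the response rates outside the 9.2 example, and the pattern of heterogeneity are assumptions.

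**1. The plan's own figure.** The documents give no expected or target c-statistic. The figure borrowed below is the 2.25, from the table of "the minimum odds ratio that can be detected with 90% power with the two-sided 0.05 level of significance". It can be checked with the usual logistic sample-size formula for a binary covariate with share B = 0.5:

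N = [1.96·√(P(1−P)/B) + 1.2816·√(P1(1−P1) + P2(1−P2)(1−B)/B)]² / [(P1−P2)²(1−B)(1−R²)]

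With P1 = 0.30, P2 = 0.3×2.25/(0.7+0.3×2.25) = 0.491, P = (0.30+0.491)/2 and R² = 0.1, N = 301.7, against 300 stated. Solving for the odds ratio at N = 300 gives 2.255. The figure reproduces, but it is an overall treatment effect, not an interaction.

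**2. Prognosis only, no heterogeneity.** Logit response = constant + s × (standard normal score), identical on both programs, overall response about 30 to 50%, 400,000 simulated patients:

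| s (assumed) | c | Gain from choosing a program |
|---|---|---|
| 0.8 | 0.70 | 0 |
| 1.0 | 0.74 | 0 |
| 1.2 | 0.77 | 0 |

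**3. Opposite effects, no prognosis.** Half the patients respond at 0.491 on EaseVRx and 0.30 on PainTRAINER, and the other half the reverse. The ratio of odds ratios is 2.25² = 5.06. With two equally common probabilities,

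c = [pA(1−pB) + ½{pA(1−pA) + pB(1−pB)}] / [(pA+pB)(2−pA−pB)] = 0.574/0.956 = 0.60,

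although the better-suited program gains 49% − 30% = 19 points for every patient. A larger crossover raises c: 0.25 vs 0.55 gives 0.66, and an extreme 0.15 vs 0.65 gives 0.76.

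**4. Both together.** Adding the step 3 heterogeneity to step 2 gives c = 0.72, 0.75 and 0.78, a rise of only 0.01 to 0.02.

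**5. Trials of 300 (1,000 simulated).** The fitted model contains treatment, covariate and interaction.

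| Scenario | Mean fitted c (95% range) | Interaction p<.10 |
|---|---|---|
| No heterogeneity, prognostic slope 1.5 | 0.82 (0.77 to 0.86) | 10.5% |
| Crossover 0.30 vs 0.50 | 0.62 (0.57 to 0.68) | 98% |

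The c-statistic orders the two cases the wrong way round. The planned interaction test separates them.

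**6. Can a benefit measure work at this size?** For a rule known in advance, the 19-point contrast with about 150 patients in each group has SE = √(0.491×0.509/150 + 0.30×0.70/150) = 5.5 points. In practice the rule is estimated. Results over 600 simulated trials (four covariates, all interactions, 10-fold cross-validation):

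| Scenario | Cross-validated c | Mean contrast (points) | Simple 95% CI above zero |
|---|---|---|---|
| No heterogeneity, slope 1.0 / 1.5 | 0.71 / 0.80 | −0.5 / +0.4 | 4 to 5% (nominal 2.5%) |
| Crossover OR 2.25 | 0.57 | 16 | 76% |
| Crossover OR 2.25 plus slope 1.0 | 0.73 | 13 | 64% |

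The contrast separates the first case at slope 1.0 from the third, where c is 0.71 against 0.73. With 6 or 14 candidate covariates and the p<.10 screen repeated inside each fold (150 trials per setting), OR 2.25 each way gave a contrast of 14 to 15 points with an SD of about 9, and the simple CI excluded zero in about 70 to 73% of trials. OR 1.5 each way (ratio 1.5² = 2.25) gave about 4 points, and the CI excluded zero in about 22 to 25%.

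**7. Joint test after screening.** With 10 covariates and no heterogeneity, a joint likelihood-ratio test at 0.05 applied to terms already selected at p<.10 gave a false-positive result in about 42% of simulated trials.

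**The case against.** The strongest reply is that section 9.4.7 never asks the c-statistic to detect heterogeneity. Interaction tests come first, with odds ratios and confidence intervals by treatment and covariate. The c-statistic is added at the end and described correctly as accuracy for response. It has no threshold, and no recommendation is made to depend on it. A reader might infer that Aim 2 stands or falls on the c-statistic, or that real opposite effects would be missed. The documents do not support that: in step 5 the planned interaction test flags the crossover in 98% of trials.

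Three further points stand:

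- The high-c case needs prognostic covariates in the final model. The text carries forward interaction terms with p<.10 and does not say whether covariates without an interaction stay in. If they do not, a purely prognostic covariate enters only by chance, about 10% of the time each.
- The illustration uses a ratio of odds ratios of about 5. Nothing in the documents supports an interaction of that size.
- The c-statistic is not literally the only check allowed, since section 9.4.1 permits Hosmer-Lemeshow. That too concerns response and not benefit.

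The reply leaves the gap itself in place: the interaction outputs take covariates singly, and nothing evaluates the combined model for choosing a program.

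**Conclusion.** The point holds in a limited form. For the final multivariable Aim 2 model, the only accuracy measure named in 9.4.7 concerns response, and no planned quantity shows whether the model helps choose a program. Under the assumptions above, c ranges from 0.70 to 0.77 with nothing to gain from choosing, if prognostic covariates are retained, and is about 0.60 with a 19-point gain for every patient. A low c is not inevitable under heterogeneity, because a very large crossover also gives a high one.

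Two stronger conclusions should be avoided. The plan does not lack a test of heterogeneity. And the 5.5-point standard error does not show that a benefit measure would be precise, because it assumes a known rule; with an estimated rule the spread was about 9 points in one set of simulations. The issue touches exploratory recommendations only and is a cheap improvement, not a threat to the primary or secondary results.

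**What to change.** In section 9.4.7:

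1. Keep the interaction tests, odds ratios and confidence intervals as planned. State whether covariates without a retained interaction stay in the final model.
2. Label the c-statistic as accuracy for predicting response, not as support for matching patients to programs.
3. Add a cross-validated benefit contrast. Repeat all screening and LASSO steps within each training fold. For each held-out patient, predict response under both programs and name the one with the higher prediction. Compare observed response between patients randomised to the named program and those randomised to the other.
4. Give the contrast a permutation test or bootstrap interval, because the simple confidence interval is too narrow.
5. If a joint interaction test is reported, apply it to a pre-specified set of treatment-by-covariate terms with a permutation p-value, not to terms already selected at p<.10.

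The cost is SAP wording and extra code; no new data are needed. The reported figure is likely to look less favourable than a c-statistic, and its precision will be limited, so it should be presented as exploratory.
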